## **8.2 PROCEDURES FOR VERIFICATION, VALIDATION AND SECURING OF ELECTRONIC DATA SYSTEMS**

An EDC system will be used in the clinical investigation. Refer to the data management plan for further details.

## **8.3 DATA RETENTION AND SPECIFIED PERIOD**

The essential clinical investigation documents shall be stored both by the Investigator and Sponsor. The location of the archived documents will be defined and documented for both parties and retained for ten (10) years after the completion of the clinical investigation.

## 9 AMENDMENTS TO THE CIP

The CIP may require to be amended during the conduct of the clinical investigation. The rationale for the amendment must be justified and assessed as to whether it is a substantial or non-substantial amendment. Amendments regarded as substantial are likely to have a significant impact on:

- The safety or physical or mental integrity of the clinical investigation participants, or,
- The scientific value of the clinical investigation.

Changes in previously approved documents are initiated by Triomed and agreed upon between the Sponsor and the Principal Investigator. Substantial amendments are submitted to the competent authorities and changes are implemented when approval is obtained. The clinical investigation documentation is updated as required and the CIP amendment log (ISF) signed by the Investigator. Triomed may at any time amend the CIP to eliminate immediate hazards to subjects. In this case the competent authority will be notified subsequently of the modifications.

## 10 DEVIATIONS FROM CLINICAL INVESTIGATION PLAN

The Investigator shall conduct the clinical investigation according to and in compliance with the CIP agreed to by Triomed and approved by the competent authorities (CA). A deviation from the CIP, is a failure to comply with the information specified in the CIP.

The Investigator shall:

- Not implement any deviation from or change the CIP without prior agreement by the Sponsor or documented approval from the regulatory authority(ies) of an amendment, except where necessary to eliminate an immediate hazard(s) to participating patients.
- Promptly notify the Sponsor and document the reasons for the deviation and if appropriate proposed protocol amendment(s) to allow expedite reporting to the regulatory authority(ies).

During the clinical investigation the monitor will document and report deviations from the CIP, GCP and applicable regulations which will be reported to Triomed. The report should include a summary of what the monitor reviewed as described in Section 6.5. Accidental protocol deviations can happen at any time and must be adequately documented and reported to the Sponsor immediately.

Frequently recurring deviations will require immediate action and could potentially be classified as a serious breach.

With finding of noncompliance to the CIP which significantly affect the patients and the scientific integrity of the clinical investigation, a root cause analysis will be performed, and appropriate corrective and preventive action taken. The Investigator will be informed in writing by Triomed of the corrective actions to be taken to avoid the reoccurrence of deviations and the corrective actions will be followed-up. If the Investigator/institution is persistently noncompliance despite corrective action by Triomed the Investigators participation in the clinical investigation will terminate. The termination of the clinical investigation due to noncompliance will be reported to the competent authorities by Triomed.

## 11 DEVICE ACCOUNTABILITY

---

The Carry Life UF system including the cycler, line set, carrying bag, storage bag, glucose solution, battery, battery charger and PD belt will only be used in the clinical investigation. The Sponsor and the Principal Investigator will keep records documenting the shipment (to and from the investigational site) and the location of all investigational devices and accessories beginning from shipment of investigational devices to the investigation sites until their return to Triomed or destruction, as applicable. The Principal Investigator will keep records documenting the hand-over or return of all investigational **devices** and accessories to/from the patient. This will be documented in the device accountability log which is contained in both the TMF and ISF and will be updated throughout the clinical investigation.

The device accountability log will include information on:

- The date of receipt and the quantities.
- Identification of each investigational device and accessory (batch number or serial number).
- Date on which the investigational device or accessory was returned and the date of return of unused, expired or malfunctioning investigational devices, and date of return of unused glucose solution.

The serial/batch numbers of the device, the line sets, and glucose solution, and the dates of use will also be documented in the patient specific eCRF page. The equipment required for the clinical investigation will be stored in a secure area at the participating sites according to the storing conditions as outlined in the respective IFUs. The monitor will verify the accountability process at each site during the site monitoring visits and at the close-out visit.

## 12 STATEMENTS OF COMPLIANCE

---

### 12.1 ETHICAL PRINCIPLES

To ensure the quality and integrity of research, this clinical investigation will be conducted according to the CIP, principles of ISO 14155:2020, EU medical device regulation (MDR) 2017/745, UK MDR 2002, the Declaration of Helsinki and its amendments, and any applicable national guidelines.

This study must be approved by the relevant competent authority and independent ethics committee (IEC) prior to enrolling participants into the study.

Any additional requirements imposed by the IEC or regulatory authority shall be followed, as appropriate.

Where applicable and consistent with local regulations and prior to consenting and enrolment of participant, the CIP, CIP amendments, Informed Consent Form (ICF), Investigator's Brochure, and other relevant documents must be submitted to an IEC and reviewed and approved by the IEC before the investigation is initiated. Any additional requirements imposed by the IEC or regulatory authority shall be followed, if appropriate. Consenting and enrolment of any patient will not start before written confirmation of approval from the relevant central or local IEC. All parties involved in the conduct of the clinical investigation shall share the responsibility for its ethical conduct in accordance with their respective roles.

### 12.2 INTERNATIONAL STANDARDS

The investigation will be performed in accordance with international standards and any regional or national regulations, as appropriate. Any additional requirements imposed by the IEC or regulatory authority shall be followed, if appropriate. The Carry Life® UF system complies with identified applicable regulatory standards, according to Appendix D in the IB.

### 12.3 START OF CLINICAL INVESTIGATION

Before the start of the clinical investigation, approval will be sought from the IEC and regulatory authority(ies) with regard to the CIP, IB, informed consent forms and other appropriate documents. Approval in writing by an IEC and regulatory authority(ies) shall be received before consenting and enrolment of any patient into the investigation. Substantial protocol amendments will be submitted by the Sponsor for review and approval by the regulatory authority(ies), and premature termination and the reasons for the decision to the regulatory authority(ies) and IEC.

### 12.4 ADDITIONAL REQUIREMENT BY EU OR REGULATORY AUTHORITY

All additional requirement imposed by EU or regulatory authorities shall be followed.

### 12.5 INSURANCE

Sponsor will maintain appropriate clinical study insurance coverage as required under applicable laws and regulations for the duration of the clinical investigation.

## 12.6 FINANCING

This clinical investigation will be financed by Triomed AB.

Investigators will provide the Sponsor with sufficient and accurate financial information as requested to allow the Sponsor to submit complete and accurate financial certification or disclosure statements to the appropriate regulatory authorities. Investigators are responsible for providing information on financial interests during the study and after completion of the study according to national regulations. All Investigators will be required to meet the requirements of applicable EU/UK regulation. Financial disclosures will be collected from all Investigators prior to their participation in the investigation.

The financial agreement between the Sponsor and the investigation sites/Investigators are addressed in a separate agreement.

All expenses arising in connection with the investigation, the remuneration of the Investigators for performance of the investigation, and the indemnification of the participants for their participation will be reimbursed in accordance with the respective contracts.

## 13 INFORMED CONSENT PROCESS

---

Prior to performing any clinical investigation activities, including screening tests and assessments, written informed consent will be obtained from subjects by signing the approved informed consent form.

During the informed consent process the Investigator shall:

1. Provide the background of the clinical investigation, the procedures involved, the risks and benefits and that participation is voluntary. Information shall be provided both verbally and in written form.
2. The patient must be given sufficient time for questions and to consider whether to participate in the clinical investigation.
3. It is the Investigators responsibility to ensure that the patient has understood the purpose of the clinical investigation before the ICF is signed.
4. A copy of the signed and dated consent form will be given to the patient, and participation shall be documented in the medical records.
5. The patient must be informed that they have the right to withdraw their consent at any time, without the need for justification and that future medical care will not be jeopardized
6. If the patient prematurely withdraws from the clinical investigation, make all reasonable effort to ascertain the reason.
4. During the clinical investigation the Investigator shall inform the patients in writing of new information that can significantly affect the patient's future health or medical care. In this case the patient has the right to re-evaluate their decision to participate, and a revised patient information and informed consent will be signed by both the Investigator and patient.
5. Provide adequate medical care for the participants during and after the investigation, in the event of adverse events and medical emergencies (Section 14.1).
6. The ICF will be retained in the ISF.

### 13.1 PATIENT CONFIDENTIALITY

Participant confidentiality and privacy are strictly held in trust by the participating Investigators, their staff, and the Sponsor. All health data collection is conducted in a manner compliant with General Data Protection Regulation (GDPR) in the European Union (EU) and applicable data privacy law. Therefore, the CIP, documentation, data, and all other information generated will be held in strict confidence. No information concerning the study, or the data will be released to any unauthorized third party without prior written approval of the Sponsor.

Confidentiality of data shall be observed by all parties involved in the clinical investigation at all times. All data shall be secured against unauthorized access and in general by:

- The patient's identification being depersonalized using a clinical investigation coded number.
- The data transferred to the Sponsor shall be in coded form.
- The privacy of the participants and confidentiality regarding information shall be preserved in reports and published data.

- The Principal Investigator will however provide direct access to source data during and after the clinical investigation for monitoring, audits, EC review and regulatory authority inspections.

The informed consent will also specify that collected data may be transferred (to either EEA countries and/or non-EEA countries). In accordance with the EU Data Protection Directive (95/46/EC), the data will not identify any patients taking part in the clinical investigation.

## 14 SAFETY

---

### 14.1 PATIENT SAFETY ASSESSMENTS DURING THE CARRY LIFE® UF STUDY SESSIONS

Foreseeable adverse events and anticipated adverse device effects are associated with excessive UF, increased IP volumes and abnormalities in plasma glucose and electrolytes and a complete description of the anticipated device effects and their mitigations can be found in Section 4.3.

#### 14.1.1 Excessive UF volumes

During the Carry Life® UF study sessions, it is expected that greater UF rates will be achieved compared to standard PD regimes. A maximum total UF volume of  $\geq 20$  ml/kg body weight/treatment has therefore been set for the Carry Life® UF study sessions.

#### 14.1.2 Clinical evaluation

Clinical symptoms indicative of fluid depletion due to excessive UF volumes shall be assessed during the in-clinic Carry Life® UF treatments. The blood pressure and heart rate are to be monitored before and after treatment and when clinically indicated.

If the systolic blood pressure is  $<100$  mmHg during the Carry Life® UF treatments the patient will be excluded from the study.

The patient will also be excluded from the rest of the study if the Carry Life® UF rate is  $>20$  ml/kg body weight/treatment.

It is at the discretion of the Investigator to discontinue the study session if or when they see fit. The Investigator shall treat the clinical symptoms which occur during the study sessions according to clinical praxis. The subject's clinical condition will be evaluated and documented in the CRF after the Carry Life® UF study session.

#### 14.1.3 Increased IP volumes

Increased IP volumes is mitigated by the automatic hourly drains during the Carry Life® UF treatments and optional additional if the patient has symptoms related increased IP volumes.

#### 14.1.4 Abnormalities in the plasma glucose and electrolyte

Patient with CKD have abnormal creatinine, urea, and electrolyte values such as potassium, despite adequate treatment for CKD. The results of the blood samples cannot be evaluated using normal values and ranges and will therefore be assessed and corrected by the Investigator according to clinical praxis. The P-glucose will also be assessed and corrected according to clinical praxis (diabetic patients). Baseline blood data will be taken during the 2nd visit and blood glucose will be taken regularly during the in-clinic visits. The baseline blood chemistry and blood glucose data during the treatment will be reviewed by the physician before allowing the subject to continue to the home phase of the study.

## 14.2 SAFETY DEFINITIONS

Throughout the course of the clinical investigation, vigilance must be maintained with regard to possible AEs and in the event of their occurrence the first concern is for the safety and well-being of the subjects.

When the ICF is signed, each subject must be informed and receive the names and telephone numbers of clinical investigation site staff for reporting AE's and medical emergencies.

Adverse events will be categorized according to EN ISO 14155:2020, Annex F, MDCG 2020-10/1 and/or national regulatory requirements.

#### 14.2.1 Adverse Event (AE)

An adverse event is any untoward medical occurrence, unintended disease or injury, or any untoward clinical signs (including an abnormal laboratory finding) in subjects, users, or other persons whether or not related to the investigational medical device.

**NOTE 1:** This definition includes events related to the investigational device or the comparator.

**NOTE 2:** This definition includes events related to the procedures involved.

**NOTE 3:** For users or other persons, this definition is restricted to events related to investigational medical devices.

#### 14.2.2 Serious Adverse Events (SAE)

A serious adverse event is defined according to the following:

1. Death,
2. Serious deterioration in the health of the subject, users, or other persons as defined by one or more of the following:
  - a life-threatening illness or injury, or
  - a permanent impairment of a body structure or a body function including chronic diseases, or
  - in-patient or prolonged hospitalization, or
  - medical or surgical intervention to prevent life-threatening illness or injury, or permanent impairment to a body structure or a body function,
3. Fetal distress, fetal death, a congenital abnormality, or birth defect including physical or mental impairment.

**NOTE 1:** Planned hospitalization for pre-existing condition, or a procedure required by the CIP, without a serious deterioration in health, is not considered a serious adverse event.

#### 14.2.3 Device deficiencies

The definition of a device deficiency is an inadequacy of a medical device related to its identity, quality, durability, usability, reliability, safety, or performance. This may include malfunctions, use error, or inadequacy in the information supplied by the manufacturer including labelling.

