**Figure 2. Clinical investigation visits**

Table 1. Schedule of activities

Visit		V1 Screening & Inclusion	V2-V4 (In-clinic treatments)	Randomization	T1-T7 (Device training)	Home treatment (two sampling days)	V5	T1-T7 (Device training)	Home treatment (two sampling days)	V6/End of study
Time point/duration	Group A, B	-14–0 Days	Week 1–2	Week 2		Week 3–6	Week 6	Week 7	Week 8–11	Week 11/After premature ending of study
	Group C, D				Week 3	Week 4–7	Week 7			
Informed consent		X								
Inclusion and exclusion criteria		X								
Demographics a		X								
Medical history b		X								
Concomitant medications c	X	X			X	X	X	X	X	
Baseline PD prescription d	X									
Fluid restriction e	X	X			X	X	X	X	X	
Randomization				X						
Vital signs & body weight f			X			X	X		X	X
Food intake and fluid intake & urinary output g			X							
Blood samples h			X				X			X
Dialysate samples i			X			X			X	
PD bags used j			X			X			X	
Fill and drain volumes k			X			X			X	
24-hour urine sample l			X (V2 only)				X			X
24-hour UF volume m						X			X	
Carry Life® UF safety assessment n			X							

Visit	V1 Screening & Inclusion	V2-V4 (In-clinic treatments)	Randomization	T1-T7 (Device training)	Home treatment (two sampling days)	V5	T1-T7 (Device training)	Home treatment (two sampling days)	V6/End of study
Transition to home evaluation		X							
Device competency assessment				X			X		
Subject clinical evaluation o					X			X	
AEs and SAEs p		X		X	X	X	X	X	X
Device malfunctions q		X		X	X		X	X	

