2) an UF rate higher than 20 ml/kg body weight/treatment.

o. Subjects will be contacted weekly for evaluation of body weight, blood pressure, volume status and clinical symptoms.

p. A nurse adequately trained in AE reporting will specifically ask the subject for occurrences of AEs and SAEs during a weekly call.

q. The nurse will specifically ask the subject for occurrences of Carry Life® UF device malfunctions weekly.

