**Cycler / system conclusion:**

All verification and validation testing performed on the Carry Life® UF cycler and system met pre-determined acceptance criteria as defined in design inputs, product specifications, and applicable standards. The cycler and system performed as expected and all testing results suggest with high statistical probability that the device will perform as intended in the clinical environment. None of the deviations from prescribed methods in the protocol adversely affected the outcome of the tests.

The previous clinical investigation Tmed-007 showed in eight PD patients that the Carry Life® UF treatment, at glucose doses between 11 g/h and 20 g/h, can be used to significantly increase the UF volume, increase the peritoneal sodium removal and increase the glucose UF efficiency (i.e., more UF per glucose amount absorbed) compared to a 2.27% CAPD dwell. The study also showed that the device was safe to use in a clinical setting when handled by PD nurses. The Carry Life® UF system is intended for use by the patient or caretaker in the home environment.

The aim for the present clinical investigation is: 1) to show that a Carry Life® UF treatment performed by the patient (or caregiver, if a caregiver normally assists the subject's PD treatment) in the home environment generates an increased UF compared to the control treatment and 2) to evaluate the overall safety of the Carry Life® UF treatment when incorporated in the subjects' current CAPD regime in the home environment and when used by the patient/caregiver in the home environment.

The proposed design of the clinical investigation is a crossover study where all subjects will perform both the control arm, which includes a baseline PD regimen including one 2.27% CAPD day dwell, and the Carry Life® UF treatment arm. Subjects will start with either the control arm or Carry Life® UF arm based on the randomization. During the Carry Life® UF arm one 2.27% glucose CAPD dwell will be replaced with Carry Life® UF treatment during three days of the week. For the remaining four days of the week, the 2.27% glucose dwell will be replaced by a 1.36% glucose dwell. With this design Triomed expect that the subject's weekly UF volume will be reasonably stable. The PD prescription can be changed as required during the study to obtain an adequate fluid removal.

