At four (4) efficacy evaluation days during the home treatment phase (two per arm), there will be a careful recording of the solution volumes used (PD solution and glucose solution), volumes drained, and samples will be taken from the drain bags after treatment. The subject, together with the responsible physician, will determine during which days and during what time of the day the efficacy evaluation treatments (the 2.27% glucose dwell during the control arm and the Carry Life® UF treatment during the Carry Life® UF arm) will be performed. For each subject all efficacy evaluation treatments shall be performed on the same day of the week and on the same time of the day. A 2.27% glucose dwell will be the comparator dwell during the control arm. In order to perform the comparator dwell and the Carry Life UF treatment during at the same time of day, the physician may

need to modify the order and duration of the CAPD day dwells during the efficacy evaluation days in the control arm home phase of the study.

AEs, SAEs, and Carry Life® UF device malfunctions will be collected throughout the study. A nurse at each participating clinic who has undergone education and training necessary for thorough AE collection will be responsible for the recording of AEs (i.e., education in good clinical practice [GCP] will be required and training with respect to the eCRF for AE reporting). In case of an AE or device malfunction in the home treatment phase, the subject will be instructed to immediately contact the clinic. Furthermore, the clinic will contact the subject weekly and specifically ask about the occurrence of any AE or Carry Life® UF device malfunction.

The patient's participation will be approximately 12 weeks. The actual time mainly depends on how frequent the three in-clinic visits are scheduled, how many training sessions are required, and the scheduling of the training visits. The study schedule will include 8 to 13 visits dependent on the individual device training requirements. Only the in-clinic visits and the visits during the home treatment phase have been assigned a specific visit number:

1. Inclusion phase – Screening & consent – Visit 1.
2. In-clinic treatment phase for dose determination efficacy and safety evaluation – Visits 2–4 (approximately 2 weeks).
3. Randomization phase – No visit.
4. Transition to home treatment phase – Visit T1 to T7 (2–7 visits, approximately 1 week).

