The subject should immediately contact the clinic if they have any questions or concerns about their clinical status or the study in general. If there are any concerns about the subject's clinical status that cannot be resolved by phone, the subject should always be brought to the clinic for a clinical assessment.

The subject will be instructed to record all clinical symptoms (AEs) and all technical issues (device malfunctions) with the Carry Life® UF system during the home treatment phase on forms which are part of a patient diary and provided to the subject before starting the home treatment phase. The

subject will be instructed to immediately contact the clinic if any clinical symptoms or technical issues with the Carry Life® UF system occur. The means of contacting the clinic will be provided.

**Efficacy evaluation days:** The efficacy evaluation days will be performed during week 2 and week 4 of each study arm during the home treatment phase, on the day (a Monday, Wednesday or Friday) and time of the day agreed. If an immediate change in a subject's prescription is required, affecting the planned efficacy evaluation day, the efficacy evaluation treatment will be postponed 2-3 days. Such occurrences will be recorded in the eCRF and indicated in the study report.

During the efficacy evaluation days the dialysate drained from the comparator 2.27% glucose dwell (control) and from the Carry Life® UF treatment will be collected by a research assistant for endpoint evaluation and analyzed according to Table 1. The 2.27% glucose control dwell will be 5 hours i.e., the same duration as the Carry Life® UF treatment.

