#### 14.6.1 Reportable events to Competent Authorities (CAs) and Ethic committees (ECs)

The following events are considered reportable to the competent authorities in accordance with the MDR requirements (Regulation (EU) 2017/745), and the MDCG 2020-10 Guidance on safety reporting in clinical investigations shall be followed:

1. Any SAE that has a causal relationship with the investigational device, the comparator or the investigation procedure or where such causal relationship is reasonably possible.
2. Any device deficiency that might have led to a SAE if:
  - Suitable action had not been taken or,
  - Intervention had not been made or,
  - If circumstances had been less fortunate.
3. New findings/updates in relation to already reported events in 1) and 2).

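### Home-phase prompts ask only about device malfunctions, although the protocol's device deficiencies also cover use error and inadequate instructions, so these are likely to be under-ascertained

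*Protocol*

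**What the plan says.** **The definition is wide.** Section 14.2.3 treats a device deficiency as an inadequacy of the device in any of several respects, usability among them, and adds: "This may include malfunctions, use error, or inadequacy in the information supplied by the manufacturer including labelling". Malfunction is one of three kinds named.

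**The duties follow the wide definition.** Section 14.4.1 has the site record every observed deficiency. Section 14.4.2 makes the investigator responsible for identifying them and sets a 24-hour limit for reporting all of them. Section 14.5 repeats both duties. Section 14.6 has the sponsor judge whether each one could have led to a serious adverse device effect. Section 14.6.1 lists as reportable to authorities "Any device deficiency that might have led to a SAE if", followed by three conditions that describe a near miss.

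**The home-phase prompts are narrow.**
- The row in Table 1 is "Device malfunctions".
- Table 1, footnote q: "The nurse will specifically ask the subject for occurrences of Carry Life® UF device malfunctions weekly".
- Section 6.1 has the clinic contact the subject weekly and "specifically ask about the occurrence of any AE or Carry Life® UF device malfunction".
- Section 6.2.5 has the subject "record all clinical symptoms (AEs) and all technical issues (device malfunctions) with the Carry Life® UF system" on diary forms.
- The lists in Section 6.4.1 for the training visits, the home phase, Visit 5 and Visit 6 all name malfunction monitoring.

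**The aim concerns home use.** Section 3.9 gives as one of two aims the overall safety of the treatment when built into the subject's regimen and "when used by the patient/caregiver in the home environment".

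**The concern.** The part of the protocol that defines and reports device problems uses one category, and the part that asks subjects about them uses a smaller one. A nurse following the text would ask whether the device had malfunctioned. She would not be led to ask whether a step was skipped, the set-up went wrong or the instructions were confusing. The diary instruction does not widen the question, because its reference to technical issues is explained in brackets as malfunctions.

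This matters because the operator at home is the patient or a caregiver. Table 6 ties contamination of the fluid path mainly to connections made by the user, and notes that each treatment with the device adds a connection. Section 3.9 reports that the summative usability study allowed no critical use errors. The sponsor thus treats use error as a safety question, yet the home prompts do not ask about it. A low count of deficiencies from the home phase could partly reflect the question that was asked.

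**Working it through.** The protocol states no figure on this point, so the check sets the texts side by side.

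**Step 1: are the two terms the same?** Section 14.2.3 lists malfunctions as one kind of deficiency, next to use error and inadequate information. Nothing in the protocol defines device malfunction as equal to device deficiency. On the document's own terms, the prompts name a subset.

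**Step 2: does any scheduled home prompt cover the rest?**

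| Source | What it asks for | Use error or unclear instructions named? |
|---|---|---|
| Table 1 row and footnote q | malfunctions | no |
| Section 6.1, weekly contact | AEs and malfunctions | no |
| Section 6.2.5, nurse contact | clinical status, AEs and malfunctions | no |
| Section 6.2.5, diary instruction | symptoms; technical issues, explained as malfunctions | no |
| Section 6.4.1, lists | AEs, SAEs and malfunctions | no |

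**Step 3: does Section 14 close the gap?** In part. Section 14.4.1 covers deficiencies that are observed. It names as routes discussion with the participant at visits, medical records, relatives and other clinicians. A use error that is mentioned or seen must be recorded. But a duty to record starts only when someone at the site becomes aware of the event, and Section 14 adds no scheduled question that would bring a silent use error to light. The gap is one of asking.

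**Step 4: how much home use is unattended?** The inputs are about 12 home treatments per subject (Section 6.2.10), about 25 subjects enrolled with a goal of 19 per-protocol completers (Section 6.3.1), and a professional present at the first home treatment to oversee set-up (Section 6.2.5).

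- All home treatments: 12 × 19 = 228 to 12 × 25 = 300.
- Without the overseen first treatment: 11 × 19 = 209 to 11 × 25 = 275.
- If staff also watched set-up on both efficacy evaluation days in the device arm: 9 × 19 = 171 to 9 × 25 = 225.

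The last line is a lower bracket, since the staff at those treatments are there to weigh bags and collect samples and need not watch set-up. The upper figures assume that all enrolled subjects reach home use, although some may be withdrawn earlier. These counts show how much use depends on self-report. They do not estimate missed events.

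**Step 5: can missed events be counted?** No. That would need a rate of use errors without an alarm or symptom, and the protocol gives none.

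**The case against.** A reader might infer that home use errors are not collected at all and that reportable near misses are never seen. The documents do not support that. Sections 14.4.1, 14.4.2 and 14.5 require deficiencies to be recorded and reported, and use error falls within the definition. Section 6.2.5 also tells subjects to contact the clinic with any question or concern about their clinical status or the study. A reader might also infer that the diary has no place for a use error. The diary form, call script and eCRF pages are not shown, so only the protocol's description of them can be judged.

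Four further objections carry weight:

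- **Classification.** A lapse in aseptic technique, which can happen at any CAPD exchange, is not plainly an inadequacy of the device. The definition says that use error may be included, so not every slip counts.
- **Reach of a question.** A set-up error that raised no alarm and that the user did not notice cannot be brought out by asking. Some errors may surface indirectly through the bag weights that subjects record, and Table 6 says treatment cannot start without priming.
- **Endpoints.** No endpoint in Section 6.2.7 and no performance claim in Section 5.3 counts deficiencies or concerns ease of use. AEs are asked about directly, and Section 14.2.5 classes an adverse event resulting from use error as an adverse device effect. It does not follow that the device would look safer on the trial's own endpoint.
- **Other safeguards.** There was a usability study with 15 nurses and 15 patients (Section 3.9), and the protocol requires a competency test before home use (Section 6.2.4) and an overseen first home treatment. These lower the risk of use error, but they do not record errors in later treatments.

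All four limit the consequence. None removes the difference between what must be reported and what is asked.

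**Conclusion.** The mismatch stands as a minor point about safety ascertainment. Section 14 makes use error and inadequate information reportable as device deficiencies, while the scheduled home-phase prompts ask only about malfunctions. These kinds of deficiency are therefore not actively solicited and are likely to be under-ascertained. What is volunteered or observed must still be recorded.

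The size of the shortfall cannot be estimated from the document. The 209 to 275 treatments after the overseen first one give the scale of reliance on self-report and nothing more. The AE and SAE endpoint, the efficacy endpoints and the reporting duties are unchanged. The conclusion assumes that call scripts and diary forms follow the protocol's wording. If those forms already ask about use errors, only the protocol text needs aligning.

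**What to change.** Replace device malfunctions with *device deficiencies (malfunctions, use errors, unclear instructions)* in the Table 1 row, footnote q, Section 6.1, Section 6.2.5, the lists in Section 6.4.1 and the diary instruction. Add one question on use errors to the existing weekly call. If the diary form and call script use the narrow wording, change them to match.

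This needs no new visit, procedure or analysis. The cost is a revision of wording and some extra minor deficiency reports, which Section 14 already requires once the site knows of the events. Errors that the user did not notice will still be missed, so any report of deficiency counts should say that they rest on self-report.
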